4.2.2 Rationale for the Use of Comparator

Placebo-controlled clinical studies for new PCVs are no longer acceptable given the proven clinical efficacy, public health impact, and widespread use of licensed PCVs worldwide. Prevnar 13™ is currently the most widely recommended vaccine for the prevention of pneumococcal disease in infants and children in many countries worldwide, includes the largest number of serotypes, and will be used as the active comparator in this study.

Refer to approved labeling for detailed background information on Prevnar 13™.

4.3 Justification for Dose

The dosing regimen of V114 is similar to that used in previous V114 adult and pediatric Phase 2 clinical studies in which 1 dose administered to adults resulted in a robust immune response and had an acceptable safety and tolerability profile.

The dose of Prevnar 13™ for use in this study is the approved dose.

4.4 Beginning and End of Study Definition

The overall study begins when the first participant signs the informed consent/assent form. The overall study ends when the last participant completes the last study-related telephone-call or visit, withdraws from the study, or is lost to follow-up (ie, the participant is unable to be contacted by the investigator).

For purposes of analysis and reporting, the overall study ends when the Sponsor receives the last laboratory result or at the time of final contact with the last participant, whichever comes last.

4.4.1 Clinical Criteria for Early Study Termination

The clinical study may be terminated early if the extent (incidence and/or severity) of emerging effects/clinical endpoints is such that the risk/benefit ratio to the study population as a whole is unacceptable. In addition, further recruitment in the study or at (a) particular study site(s) may be stopped due to insufficient compliance with the protocol, Good Clinical Practice (GCP), and/or other applicable regulatory requirements, procedure-related problems or an unacceptably high number of discontinuations or withdrawals due to administrative reasons.

5 STUDY POPULATION

Male/Female participants with SCD between the ages of 5 and 17 years (inclusive) will be enrolled in this study.

Prospective approval of protocol deviations to recruitment and enrollment criteria, also known as protocol waivers or exemptions, is not permitted.

5.1 Inclusion Criteria

To be eligible for inclusion in this study, the participant must:

1. Have a documented diagnosis of SCD in their medical record.

Demographics

2. Be male or female, from 5 years to 17 years of age (inclusive), at the time of obtaining the informed consent/assent.

Female Participants

3. Not be pregnant (Appendix 5) or breastfeeding, and at least 1 of the following conditions applies:
 - a. Not be a woman of childbearing potential (WOCBP) as defined in Appendix 5.
OR
 - b. A WOCBP must agree to follow the contraceptive guidance in Appendix 5 during the treatment period and for at least 6 weeks after the last dose of study intervention.

Informed Consent/Assent

4. Have a legally acceptable representative who understands the study procedures, alternate treatments available, and risks involved with the study and voluntarily agrees to participate by giving written informed consent/assent. The legally acceptable representative may also provide consent/assent for future biomedical research. However, the participant may participate in the main study without participating in future biomedical research.

5.2 Exclusion Criteria

The participant must be excluded from the study if the participant:

Medical Conditions

1. Has a history of IPD (positive blood culture, positive cerebrospinal fluid culture, or positive culture at another sterile site) or known history of other culture-positive pneumococcal disease within 3 years of Visit 1 (Day 1).
2. Has a known hypersensitivity to any component of pneumococcal conjugate vaccine (PCV), or any diphtheria toxoid-containing vaccine.
3. Has a known or suspected impairment of immunological function.
4. Has a history of congenital or acquired immunodeficiency.
5. Has a documented human immunodeficiency virus (HIV) infection.
6. Has a history of autoimmune disease (including but not limited to systemic lupus erythematosus, antiphospholipid syndrome, Behcet's disease, autoimmune thyroid disease, polymyositis and dermatomyositis, scleroderma, or type 1 diabetes mellitus).
7. Has a known coagulation disorder contraindicating intramuscular vaccination.
8. *Has had a recent febrile illness (defined as oral or tympanic temperature $\geq 38.1^{\circ}\text{C}$ [$\geq 100.5^{\circ}\text{F}$]; axillary or temporal temperature $\geq 37.8^{\circ}\text{C}$ [$\geq 100.0^{\circ}\text{F}$]) or received antibiotic therapy for any acute illness occurring within 72 hours before receipt of study vaccine.
9. Has a history of malignancy ≤ 5 years prior to signing informed consent/assent, except for adequately treated basal cell or squamous cell skin cancer or in situ cervical cancer.
10. Is a WOCBP who has a positive urine or serum pregnancy test before the first vaccination at Visit 1 (Day 1).

Prior/Concomitant Therapy

11. Has received any PCV or PnPs vaccine <3 years before Visit 1 (Day 1).
12. Is 5 years of age and has received <3 doses of PCV.
13. *Meets one or more of the following systemic corticosteroid exclusion criteria:
 - a. Has received systemic corticosteroids (prednisone equivalent of ≥ 20 mg/day) for ≥ 14 consecutive days and has not completed treatment at least 30 days before study vaccination.

- b. Has received systemic corticosteroids exceeding physiologic replacement doses (approximately 5 mg/day prednisone equivalent) within 14 days before study vaccination.
- c. Is expected to require systemic corticosteroids within 30 days after study vaccination.

Note: Topical, ophthalmic, intra-articular or soft-tissue (eg, bursa, tendon steroid injections), and inhaled/nebulized steroids are permitted.

14. Is receiving immunosuppressive therapy, including chemotherapeutic agents used to treat cancer or other conditions, and interventions associated with organ or bone marrow transplantation, or autoimmune disease.

Note: Hydroxyurea is permitted.

15. *Has received any non-live vaccine within the 14 days before receipt of the study vaccine or is scheduled to receive any non-live vaccine within 30 days following receipt of the study vaccine. **Exceptions:** Inactivated influenza vaccine may be administered but must be given at least 7 days before receipt of the study vaccine or at least 15 days after receipt of the study vaccine. PNEUMOVAX™23 may be administered after the blood draw at Visit 2 (Day 30).

16. *Has received any live vaccine within 30 days before receipt of the study vaccine or is scheduled to receive any live vaccine within 30 days following receipt of the study vaccine.

17. Has received immunoglobulin within 6 months before receipt of study vaccine.

Prior/Concurrent Clinical Study Experience

18. Has participated in another clinical study of an investigational product within 2 months before the beginning or anytime during the duration of the current clinical study. Participants enrolled in observational studies may be included; these will be reviewed on a case-by-case basis for approval by the Sponsor.

Other Exclusions

- 19. Has a recent history (within the last year) of more than 3 inpatient hospitalizations.
- 20. Is, at the time of signing informed consent/assent, a user of recreational or illicit drugs or has had a recent history (within the last year) of drug or alcohol abuse or dependence as assessed by the study investigator.
- 21. Has a history or current evidence of any condition, therapy, lab abnormality or other circumstance that might expose the participant to risk by participating in the study, confound the results of the study, or interfere with the participant's participation for the full duration of the study in the opinion of the Investigator.

22. Is or has an immediate family member (eg, spouse, parent/legal guardian, sibling, or child) who is investigational site or Sponsor staff directly involved with this study.

For items with an asterisk (*), if the participant meets these exclusion criteria, Visit 1 may be rescheduled for a time when these criteria are not met.

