2.1 Study Rationale

Sickle cell disease (SCD) is a group of disorders caused by abnormal hemoglobin which can deform or “sickle” red blood cells and lead to end-organ damage. Children with SCD have an increased risk of invasive disease caused by encapsulated bacteria, such as *Streptococcus pneumoniae*, secondary to splenic dysfunction and abnormalities of innate immunity. Early interventions with vaccinations against encapsulated bacteria have significantly reduced the mortality of SCD in the United States and Europe [Quinn, C. T., et al 2010] [Telfer, P., et al 2007].

Immunization guidelines recommend that infants and children with SCD follow the same PCV schedule as healthy infants and children up to 5 years of age, including catch up vaccination. Children with SCD 2 to 18 years of age, without a history of immunization with the 13-valent Prevnar 13™ are recommended to receive catch up immunization with Prevnar 13™, regardless of previous immunization with other PCVs containing fewer pneumococcal polysaccharide (PnPs) serotypes. In addition, it is recommended that children with SCD receive 2 doses of the 23-valent PnPs vaccine, PNEUMOVAX™23; the first dose at 2 years of age and the second dose either at 5 years of age [National Heart, Lung and Blood Institute 2014] or at 7 years of age (5 years after first dose) [Centers for Disease Control and Prevention (CDC) 2013].

This clinical study is designed to describe the safety, tolerability, and immunogenicity of V114 compared with Prevnar 13™ in children with SCD 5 to 17 years of age (inclusive) who are either PCV naïve or have a history of previous PCV immunization. Because of widespread adherence to immunization guidelines for children with SCD, it is anticipated that a majority of participants will have been previously vaccinated with a PCV. Safety and immunogenicity data collected in this study will support recommendations for V114 catch-up vaccination in children who received a PCV containing fewer than 15 serotypes or who are PCV naïve. In addition, the data from this study will contribute to the overall safety database and immunogenicity profile of V114 in children.

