2.2.3 Information on Other Study-related Therapy

Refer to approved labeling for detailed background information on Prevnar 13TM.

Prevnr 13TM is a pneumococcal conjugate vaccine that contains the 7 pneumococcal serotypes included in PrevnarTM (4, 6B, 9V, 14, 18C, 19F, 23F) plus 6 additional serotypes (1, 3, 5, 6A, 7F, and 19A). In many countries, Prevnar 13TM is given as a part of routine immunization schedules for all infants and children 2 to 59 months of age. Children with SCD 2 to 18 years of age, without a history of immunization with Prevnar 13TM are recommended to receive catch up immunization with Prevnar 13TM, regardless of previous immunization with other PCVs containing fewer PnPs serotypes. [Centers for Disease Control and Prevention (CDC) 2013].

PrevnrTM and Prevnar 13TM are also known as PrevenarTM and Prevenar 13TM in many countries outside of the United States; these vaccines will be referred to as PrevnarTM and Prevnar 13TM throughout this document.

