8.1.2 Inclusion/Exclusion Criteria

All inclusion and exclusion criteria will be reviewed by the investigator, who is a qualified physician, to ensure that the participant qualifies for the study. The investigator should consult with the Sponsor's Clinical Director for any questions about participant eligibility.

If the participant meets any of the exclusion criteria with an asterisk (*), Visit 1 (Day 1) may be rescheduled for a time when these criteria are not met.

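### Does the exclusion for impaired immune function shut out the children with sickle cell disease whom the trial is meant to enrol?

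*Combined protocol and SAP*

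**What the plan says.** Section 5.2 lists 22 mandatory exclusions. Item 3 applies to a child who "Has a known or suspected impairment of immunological function", and item 4 to one who "Has a history of congenital or acquired immunodeficiency". Neither carries a definition, a note or an exception for SCD, and neither has the asterisk that allows Visit 1 to be rescheduled.

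Section 2.1 says that the increased risk of invasive disease in children with SCD is "secondary to splenic dysfunction and abnormalities of innate immunity". Inclusion criterion 1 in Section 5.1 is "Have a documented diagnosis of SCD in their medical record"; it sets no condition on genotype, spleen or immune status.

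Three other places bear on the reading:
- Item 14 of Section 5.2 excludes children on immunosuppressive therapy but adds "Note: Hydroxyurea is permitted".
- Section 5 states "Prospective approval of protocol deviations to recruitment and enrollment criteria, also known as protocol waivers or exemptions, is not permitted".
- Section 8.1.2 tells the investigator to consult the Sponsor's "Clinical Director for any questions about participant eligibility".

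The sSAP says nothing on the point.

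**The concern.** The disease that qualifies a child for the trial is, on the protocol's own account, also a reason to suspect impaired immunity. Item 3 is mandatory and covers suspicion as well as knowledge. An investigator faced with a child whose SCD-related loss of splenic function is on record could exclude the child on the words of item 3, or enrol the child because the impairment is part of SCD.

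Section 4.2 intends the data to support catch-up recommendations in children with SCD. If some sites screened out the more impaired children, the within-group antibody summaries would describe a less impaired subset without saying so. A second worry is that an enrolled child might later be disputed as an eligibility deviation, in a trial that expects only about 54 and 26 evaluable participants for the per-protocol immunogenicity analysis.

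**Working it through.** The point rests on wording, so the check sets the passages side by side. The plan states no figure that needs reproducing.

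**1. Does impairment intrinsic to SCD trigger item 3?** There are two consistent answers.
- Suppose it does. Section 2.1 gives grounds to suspect such impairment in children with SCD as a group, and suspicion is enough under item 3. The eligible number would then be essentially 0, against 67 + 33 = 100 planned. This contradicts the title, Section 5, inclusion criterion 1 and the sample size.
- Suppose it does not. Item 3 then covers impairment from some other source, and every other section agrees with it.

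**2. Is there a stable middle reading, in which only documented SCD-related impairment excludes?** Item 3 treats known and suspected impairment alike. A line between a child whose splenic dysfunction is recorded and one in whom it is presumed does not come from the text. Asplenia and splenectomy are not mentioned anywhere in the documents; they would be a reader's own examples.

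**3. What does the context add?** The items around item 3 deal with HIV, autoimmune disease and immunosuppressive treatment, all of which are sources of impairment separate from SCD. The hydroxyurea note shows that the drafters adapted at least one immune-related exclusion to this population. Section 2.2.3 describes the catch-up recommendation as applying to "Children with SCD 2 to 18 years of age" who have not had Prevnar 13, with no division by splenic status.

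**4. Does the bar on waivers block clarification?** No. Section 5 forbids advance approval of a departure from a criterion. Asking what a criterion means is not a request to depart from it, and Section 8.1.2 provides for that question.

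**5. Would any planned result change?**
- Eligibility is decided before randomisation, so the reading of item 3 cannot bias one arm against the other.
- The primary summaries are within-group geometric means with t-based intervals. Their formulae, and the interval table in Section 9.9.1, do not depend on how item 3 is read.
- The potential per-protocol exclusions listed in protocol Section 9.5.1 and sSAP Section 3.5.1 concern failure to receive vaccine, incorrect vaccine, prohibited medication or vaccine, and sampling outside the window. Eligibility disputes are not on the list, although it is not stated to be exhaustive.
- The supportive Full Analysis Set for the primary IgG endpoint keeps every vaccinated participant with a serology result at the time point, so a disputed child with a Day 30 result stays in that analysis.

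**6. Can the effect on generalisability be sized?** No. The documents give no proportion with documented splenic impairment and no response by splenic status. The absence of stratification (Section 6.3.2) and of a splenic subgroup among the four factors in sSAP Section 3.10 does not help: the same holds for any characteristic on which the trial neither stratifies nor reports.

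**The case for a change.** The best case for a change is that the drafters wrote an exception where they wanted one, for hydroxyurea, so silence in items 3 and 4 may be taken as deliberate. Section 2.1 speaks of a group and does not say that every child is affected, so a cautious investigator could still judge suspicion child by child. The consultation route helps only if a site notices the ambiguity and asks. Splenic status is not a named baseline characteristic, so selective enrolment might never show in the report. A clarifying clause would cost almost nothing.

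Part of this stands. The text is silent, and some variation between sites is possible. The hydroxyurea note cuts both ways, since it also shows that immune-related exclusions were written with SCD in mind. Section 9.6.3 provides for baseline characteristics without listing them all, so splenic status may be tabulated under the plan as it is. Such a table would be imperfect, because the medical history in Section 8.1.4 reaches back only 5 years, and it would alter no estimate. Nothing in the documents shows that any child would be turned away. The protocol also narrows the SCD population on purpose elsewhere, for example by excluding children with more than 3 inpatient stays in the past year (item 19), so the trial does not claim to represent every child with SCD.

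**Conclusion.** The overlap between item 3 and Section 2.1 is real as a matter of wording, and item 4 shares the gap. It does not call for a change. The only reading consistent with the title, Section 5, inclusion criterion 1 and a planned 100 participants is that item 3 concerns impairment beyond SCD itself, and sites in doubt have one sponsor role to ask. No between-arm bias arises and no stated figure is shown to be wrong. The effect on the antibody summaries is unquantified and cannot be quantified from the documents.

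This conclusion assumes that sites read item 3 together with the inclusion criteria and that the sponsor answers eligibility questions consistently. If screening logs showed children being refused under item 3 because of SCD-related impairment, the point would need to be reopened.

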5.3 Lifestyle Considerations

No lifestyle restrictions are required.

5.4 Screen Failures

Screen failures are defined as participants who consent/assent to participate in the clinical study, but are not subsequently randomized in the study. A minimal set of screen failure information is required to ensure transparent reporting of screen failure participants to meet the Consolidated Standards of Reporting Trials (CONSORT) publishing requirements and to respond to queries from regulatory authorities. Minimal information includes demography, screen failure details, eligibility criteria, and any AEs or SAEs meeting reporting requirements as outlined in the data entry guidelines.

5.5 Participant Replacement Strategy

A participant who withdraws from the study will not be replaced.

6 STUDY INTERVENTION

Study intervention is defined as any investigational intervention(s), marketed product(s), placebo, or medical device(s) intended to be administered to a study participant according to the study protocol.

Clinical supplies (V114 and Prevnar 13TM) will be packaged to support enrollment. Clinical supplies will be affixed with a clinical label in accordance with regulatory requirements.

6.1 Study Intervention(s) Administered

The study interventions to be used in this study are outlined in [Table 1](#).

Table 1 Study Interventions

Arm Name	Arm Type	Intervention Name	Type	Dose Formulation	Unit Dose Strength(s)	Dosage Level(s)	Route of Admin	Vaccination Regimen	Use	IMP/ NIMP	Sourcing
V114	Experimental	V114	Biological/ Vaccine	Sterile Suspension	Refer to IB	0.5 mL	IM	Single Dose at Visit 1 (Day 1)	Experimental	IMP	Central
Prevnar 13™	Active Comparator	Prevnar 13™	Biological/ Vaccine	Sterile Suspension	Refer to product labeling	0.5 mL	IM	Single Dose at Visit 1 (Day 1)	Experimental	IMP	Central

Admin = administration; IB = Investigator's Brochure; IM = intramuscular; IMP = investigational medicinal product; NIMP = non-investigational medicinal product.

Definitions of Investigational Medicinal Product (IMP) and Non-Investigational Medicinal Product (NIMP) are based on guidance issued by the European Commission. Regional and/or Country differences of the definition of IMP/NIMP may exist. In these circumstances, local legislation is followed.

All supplies indicated in [Table 1](#) will be provided per the "Sourcing" column depending upon local country operational requirements. If local sourcing, every attempt should be made to source these supplies from a single lot/batch number where possible (eg, not applicable in the case where multiple lots or batches may be required due to the length of the study, etc).

Refer to Section 8.1.8 for details regarding administration of the study intervention.

6.2 Preparation/Handling/Storage/Accountability

6.2.1 Dose Preparation

There are no specific calculations or evaluations required to be performed in order to administer the proper dose to each participant. The rationale for selection of doses to be used in this study is provided in Section 4.3.

6.2.2 Handling, Storage, and Accountability

The investigator or designee must confirm appropriate temperature conditions have been maintained during transit for all study intervention received, and any discrepancies are reported and resolved before use of the study intervention.

Only participants enrolled in the study may receive study intervention, and only authorized site staff may supply or administer study intervention. All study interventions must be stored in a secure, environmentally controlled, and monitored (manual or automated) area in accordance with the labeled storage conditions with access limited to authorized site staff.

The investigator, institution, or the head of the medical institution (where applicable) is responsible for study intervention accountability, reconciliation, and record maintenance (ie, receipt, reconciliation, and final disposition records).

For all study sites, the local country Sponsor personnel or designee will provide appropriate documentation that must be completed for drug accountability and return, or local discard and destruction if appropriate. Where local discard and destruction is appropriate, the investigator is responsible for ensuring that a local discard/destruction procedure is documented.

The study site is responsible for recording the lot number, manufacturer, and expiry date for any locally purchased product (if applicable) as per local guidelines unless otherwise instructed by the Sponsor.

The investigator shall take responsibility for and shall take all steps to maintain appropriate records and ensure appropriate supply, storage, handling, distribution, and usage of study interventions in accordance with the protocol and any applicable laws and regulations.

